5.4.3.3 Relationship of Adverse Events to Study Treatment

Relationship of an AE to the Investigational Product (IP), the enema procedure, *C. difficile* disease, and a preexisting condition will be classified by the investigator as definite, probable, possible, or unrelated. Related events will include AEs that are classified as definitely, probably, or possibly related.

5.4.3.4 Treatment-Emergent Adverse Events

Adverse events will be considered treatment-emergent adverse events (TEAE) according to the following algorithm:

- If the complete onset date of an AE is known, then:
 - If AE onset date is prior to initial treatment date, then the AE will not be considered treatment-emergent.

- If AE onset date occurs after IP exposure on or after initial treatment date, then the AE will be considered treatment-emergent.
 - If AE onset date is partially known, then:
 - If day is unknown, and month/year occurs on or after first enema month/year, then AE will be considered treatment-emergent. Otherwise, AE will not be considered treatment-emergent.
 - If month/day is unknown, and year occurs on or after first enema year, then AE will be considered treatment-emergent. Otherwise, AE will not be considered treatment-emergent.

5.4.4 *Other Observations Related to Safety*

5.4.4.1 *Solicited Adverse Events*

The following list of anticipated adverse events are solicited from subjects via the Subject Diary from the date of enrollment through the 7th day after receiving the study treatment.:

- gas (flatulence)
- abdominal distension or bloating
- rectal irritation or pain
- chills/severe shivering
- abdominal pain or cramping
- increased diarrhea
- constipation
- rectal bleeding
- nausea
- vomiting
- fever $\geq 37.8^{\circ}\text{C}$ ($\geq 100.0^{\circ}\text{F}$)

Frequency and severity of the solicited AEs will also be captured in the Subject Diary.

5.4.4.2 *Major Complications of CDI Events*

Frequencies of major complications of CDI including death, septic shock, toxic megacolon, colonic perforation, emergency colectomy, or ICU admission will be collected through the 6-month telephone assessment after the last study enema.

5.4.4.3 *Hospitalizations for Recurrent CDI*

Details regarding hospitalizations due to CDI, including admission and discharge date/time, reason for admission, whether the subject was admitted to an ICU, and ICU admission and discharge date/time (if applicable), will be collected following both the first and second study enemas

5.5 **Efficacy Variables**

5.5.1 ***Efficacy Endpoint***

Assessment of secondary objectives will include descriptive statistics and be performed on pre-defined analysis populations including Intent-to-Treat (ITT), modified Intent-to-Treat (mITT) and Per-Protocol (PP). Additional sub-analyses of safety data may be performed on sub-populations.

1. **Efficacy Endpoint:** Recurrence of CDI within 8 weeks of treatment.

Recurrence of CDI after 8 weeks from completion of the study treatment is considered a new *C. difficile* infection.

The efficacy parameter used to determine treatment success is defined as the absence of CDI diarrhea through 8 weeks after completing a study treatment. Efficacy assessments will occur at each scheduled office visit: 1-, 4- and 8-weeks.

2. **Efficacy Endpoint:** Loss of sustained clinical response through 6 months after treatment

Sustained clinical response is defined as treatment success of the presenting CDI recurrence and no new CDI episodes through 6 months after completing a study treatment. Efficacy assessments will occur at each scheduled phone assessment: 4 and 6 months.

5.6 **Other Endpoints**

Other endpoints include the following:

1. Baseline characteristics: sex, age, number of prior CDI events, race, ethnicity
2. Subject fecal microbial composition at Screening, 1-week, 4-weeks, 8-weeks, 4 months, and 6 months after study treatment
3. Cdif32 questionnaire at Screening, 1-week, 8-weeks, 4 months, and 6 months

4. Recurrence of CDI within 8 weeks of a second RBX2660 treatment
5. Concentration of vancomycin resistant enterococcus in stool samples for subjects who were carriers at Baseline at 1-week, 4-weeks, 8-weeks, 4 months, and 6 months after study treatment.
6. Presence of *C. difficile* in stool samples at Screening, 1-week, 4-weeks, 8-weeks, 4 months, and 6 months after study treatment

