Adverse events were collected for each subject by the investigational sites and solicited via a subject diary from the point of enrollment (information consent) through study exit. Safety results were analyzed using the SP, which consisted of any subject who had an attempted study drug administration (N=128), whether placebo or RBX2660. There

were 907 AEs reported by 106 subjects. Of those AEs, 841 events in 105 subjects occurred after administration of study IP and are termed treatment emergent adverse events (TEAEs). The TEAEs reported were mostly mild-to-moderate in severity (87.6%) and were primarily related to gastrointestinal disorders (32.5%) as would be expected in this population.

Overall Results

These results indicate that one or two doses of RBX2660 is a safe and potentially effective therapy for rCDI.

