11.1. Adverse Event Management

Adverse events (AE), which include clinical laboratory test variables, will be monitored and documented from the time of informed consent. Subjects should be instructed to report any AE that they experience to the investigator. Investigators should make an assessment for AEs at each visit and record the event on the appropriate eCRF.

Wherever possible, a specific disease or syndrome rather than individual associated signs and symptoms should be identified by the investigator and recorded on the eCRF. However, if an observed or reported sign or symptom is not considered a component of a specific disease or syndrome by the investigator, it should be recorded as a separate adverse event on the eCRF. Additionally, the condition that led to a medical or surgical procedure (e.g., surgery, endoscopy, tooth extraction, or transfusion) should be recorded as an AE, not the procedure.

Any medical condition already present at Screening should not be reported as an AE unless the medical condition or signs or symptoms present at Screening change in severity or seriousness at any time during the study. In this case, it should be reported as an AE.

Clinically significant abnormal laboratory or other examination (e.g., electrocardiogram) findings that are detected during the study or are present at Screening and significantly worsen during the study should be assessed for an AE. The investigator will exercise their medical and scientific judgment in deciding whether an abnormal laboratory finding or other abnormal assessment is clinically significant. Clinically significant abnormal laboratory values occurring during the clinical study will be followed until repeat tests return to normal, stabilize, or are no longer clinically significant. Any abnormal test that is determined to be an error does not require reporting as an AE.

For all CDI recurrences, information is recorded on the Follow-up eCRF and applicable CDI eCRF. Recurrence of CDI is not to be reported as an AE unless hospitalization \geq 24 hours is required as part of treatment. If hospitalization \geq 24 hours is required, the event qualifies as an AE and is to be reported as an SAE (see **Section 11.14** for sponsor reporting requirements).

AEs should be followed until the event resolves or the subject exits the study. Chronic condition is defined as a condition lasting > 3 months.

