11.5. Preexisting Condition

A preexisting condition, including abnormal physical exam findings, is one that is present at the start of the study and is to be recorded at the time of the Screening visit. A preexisting condition is only to be recorded as an adverse event if the frequency, intensity or the character of the condition worsens during study participation.

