5.4 Safety Variables

Assessment of the primary safety objective and other safety objectives will be performed on all subjects exposed to RBX2660 (Safety Population, see Section 6.3.1), and will include descriptive statistics. Additional sub-analyses of safety data may be performed on sub-populations.

5.4.1 *Primary Safety Endpoint*

Number of subjects with investigational product- and/or enema-related treatment-emergent adverse events (TEAEs).

5.4.2 *Other Safety Endpoints*

1. Number of adverse events per subject
2. Timing of attributable TEAEs
3. Duration of TEAEs
4. Relatedness of TEAEs
5. Severity of TEAEs
6. Causality of TEAEs to IP, enema, *C. difficile* or prior condition
7. Number of each of the following CDI-related TEAEs through 8-weeks post treatment: death, septic shock, toxic megacolon, colonic perforation, emergency colectomy, and intensive care unit (ICU) admission
8. Onset of new chronic conditions relative to treatment administration

5.4.3 *Adverse Events*

An adverse event (AE) is any untoward medical occurrence associated with the use of IP, whether or not the event is considered product-related. Preexisting conditions that worsen in frequency, intensity or character of the condition during study participation will be recorded as an AE. AEs will be recorded for each subject from the day of enrollment through the 6-month telephone assessment. Serious adverse events (SAEs) will be recorded for each subject from the day of enrollment through the duration of the study.

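### The TEAE rule looks only at onset date, so an adverse event that starts between consent and the first enema and worsens afterwards counts towards the primary endpoint only if the site chooses to record the worsening as a new event

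*SAP*

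**What the plan says.** **The TEAE rule.** SAP 5.4.3.4 tests onset date and nothing else. For complete dates: "If AE onset date is prior to initial treatment date, then the AE will not be considered treatment-emergent", and "If AE onset date occurs after IP exposure on or after initial treatment date, then the AE will be considered treatment-emergent". For partial dates: "If day is unknown, and month/year occurs on or after first enema month/year, then AE will be considered treatment-emergent"; a parallel rule applies when only the year is known. There is no clause on worsening, and the protocol gives no other TEAE definition for this study.

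**What depends on it.** The primary endpoint (protocol 6.4, SAP 5.4.1) is the number of subjects with a TEAE related to the product and/or the enema. The TEAE tables by severity, relatedness and seriousness in SAP 6.6.2.1 use the same flag.

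**When AEs are collected.** Protocol 11.1 says that AEs "will be monitored and documented from the time of informed consent", and SAP 5.4.3 agrees: "AEs will be recorded for each subject from the day of enrollment through the 6-month telephone assessment". Protocol 9.3 allows up to 21 days from Screening to enema.

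**Rules on worsening.** Protocol 11.1 makes a condition already there at Screening reportable if it changes in severity or seriousness. Protocol 11.5 does the same for a preexisting condition, which "is one that is present at the start of the study and is to be recorded at the time of the Screening visit". SAP 5.4.3 repeats the rule for preexisting conditions. Footnote 2 to protocol Table 10-1, repeated under the SAP 5.1 schedule, asks that a solicited symptom graded worse than at Screening be considered as a potential AE.

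**The concern.** A TEAE definition normally has two limbs: events that begin after treatment, and events that were there before and get worse after it. This SAP has only the first. The interval left open runs from consent to the enema and includes the 24-72 hour antibiotic washout, when bowel symptoms could plausibly start. Those are also the kind of symptoms that protocol 11.3 lists as anticipated.

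The study is single-arm and unblinded, and its main product is a descriptive safety count. No control arm carries the same omission. If product-related worsening is left out of that count, or is included at some sites and not at others, the headline figure is affected directly.

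**Working it through.** The plan states no figure to reproduce: 750 is a treatment cap with no power calculation behind it (SAP 3.3). The check has three steps.

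**1. Apply the rule to test dates.** Take an enema on 18 June (illustrative).

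| Recorded AE onset | TEAE under SAP 5.4.3.4? |
|---|---|
| 10 June | No, whatever happens later |
| 17 June | No, whatever happens later |
| 18 June, after exposure | Yes |
| June, day missing | Yes, even if it began before the enema |
| May, day missing | No |
| Same year, month and day missing | Yes, even if it began before the enema |

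A known pre-enema onset is excluded regardless of worsening, while an imprecise one in the enema month is included.

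**2. See whether another section closes the gap.**
- Protocol 11.1 and 11.5 and SAP 5.4.3 cover what was present at Screening or study start. They decide whether an AE is recorded, not whether it is treatment-emergent.
- Footnote 2 covers only the 11 solicited diary symptoms, up to the day before the 1-week visit. It asks for an assessment and requires neither a new record nor a new onset date.
- Protocol 11.1 has AEs followed until they resolve or the subject exits, which fits one continuing record with its first onset date.
- SAP 6.6.2.1 places AEs with pre-enema onset in the Baseline interval.

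Example: mild cramping starts two days before the enema and becomes severe hours after it. A site that enters the severe episode as a new AE on the enema day produces a TEAE. A site that updates the severity on the existing record does not. The documents permit both.

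**3. Size.** Pool of AEs with pre-enema onset, taken as all AEs minus TEAEs in the two earlier studies that report both (protocol 5.3.2 and 5.3.3):
- Study 2014-01: 907 - 841 = 66; 66/128 = 0.52 per exposed subject (placebo subjects included); 0.516 × 750 = 387.
- Study 2015-01, RBX2660 arm: 879 - 805 = 74; 74/149 = 0.50 per treated subject; 0.497 × 750 = 372.

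So about 370 to 390 such AEs might be expected at 750 treated. The documents do not say what share worsens after dosing, or what share of those is judged related.

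The endpoint counts subjects. Let *f* be the assumed share of treated subjects with a related post-enema worsening of this kind and no other related TEAE. The primary count then rises by 750 × *f*. As an illustrative base, study 2019-02 (protocol 5.3.5) had 11 subjects (17.2%) with a product-related TEAE, which implies 64 subjects; 11/64 × 750 = 129.

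| Assumed *f* | Extra subjects of 750 | Rate (base 17.2%) |
|---|---|---|
| 0.5% | 3.75, about 4 | 17.7% |
| 1% | 7.5, about 8 | 18.2% |
| 2% | 15 | 19.2% |
| 5% | 37.5, about 38 | 22.2% |

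For scale, the 95% half-width of a 17.2% rate in 750 subjects is 1.96 × √(0.172 × 0.828/750) = 2.7 percentage points.

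**The case against.** The strongest reply is that the plan already catches much of this. Footnote 2 applies to the cramping example, because cramping is a solicited symptom. Protocol 11.8 encourages investigators who are unsure to enter a finding as an AE. An investigator who judges the worsening related is judging something that happened after the enema, and may well record it with a post-enema onset; it would then be a TEAE. This stands as far as it goes: some worsened events will be captured. It does not close the gap, because nothing requires the new record and unsolicited events have no such prompt.

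Second, the worsening is visible elsewhere. SAP 6.6.2.5 tabulates diary severity on the enema day and through week 1, plus the post-treatment maximum, and its categorical baseline is the last value before the enema. The all-AE summaries, onset-interval tables and listings keep pre-enema onsets. This is correct, so a reader should not infer that these harms disappear from the report. But the diary tables carry no relatedness assessment and do not feed the primary count.

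Third, the effect on subjects may be small. In each earlier study, subjects with any AE exceeded subjects with any TEAE by one (106 against 105; 124 against 123), so pre-enema AEs rarely stood alone. This is fair, although it concerns TEAEs of any cause, not related ones.

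**Conclusion.** The definition has a real gap, and it reaches the primary endpoint. An AE with a complete onset date between consent and the first enema that worsens or becomes serious after the enema is not treatment-emergent unless the site chooses to enter the worsening separately. The related-TEAE count, and the TEAE tables by severity, relatedness and seriousness, can be understated and depend on recording habit across about 80 sites.

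The size is unknown and possibly small. A subject is lost only if no other related TEAE is present. The table above rests on assumed values of *f*; at 2% or less the change is smaller than the sampling half-width.

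Two stronger readings are not supported. One is that such an event can never be a TEAE: the partial-date rule counts some pre-enema onsets, and a new record would count. The other is a firm number of lost events. Assuming that 5% to 20% of the pre-enema pool worsens would give about 19 to 77 (0.05 × 372 and 0.20 × 387), but that share is not in the documents. The result also counts events of any cause, whereas the endpoint counts subjects with a related TEAE.

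**What to change.** Two changes, which need to be made together because the first relies on a date that the second collects.

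1. In SAP 5.4.3.4, add: an AE with onset before the first enema that increases in severity, or becomes serious, on or after the first enema is treatment-emergent, with the date of worsening as its onset date.
2. In protocol 11.1 and the eCRF completion guidelines, instruct sites to enter such worsening as a new AE dated at the worsening, with its own relatedness assessment. State that this includes solicited symptoms found to have worsened under footnote 2 of Table 10-1.

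The cost is one SAP sentence, one recording instruction and a little more data entry. The related-TEAE count may rise slightly. Comparability with earlier RBX2660 studies falls slightly if they used an onset-only definition; protocol 5.3.2 describes the 2014-01 TEAEs simply as events after administration ("841 events in 105 subjects occurred after administration of study IP"). A supplementary count on onset date alone would preserve that comparison.

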6 STATISTICAL ANALYSIS

6.1 Disposition of Subjects

A summary table will present subject disposition for all subjects enrolled. The table will show the number of subjects enrolled (consented), the number of enrolled subjects not treated, and the number of subjects treated. The proportion of subjects who complete the study and who discontinue the study will be presented. Separately, a table or listing will be created to document the subjects that are included in each analysis population.

Discontinuation will be categorized by reason as a percentage of the number of subjects in each analysis population and overall. Additionally, subjects who were successfully treated but withdrew prior to the 8-week efficacy endpoint evaluation will be identified along with the reason for withdrawal to document which analysis population(s) to which they contribute.

6.2 Protocol Deviations

Protocol deviations will be tracked. The information available will be summarized by deviation type and listed by individual site.

6.3 Baseline Assessments

Baseline assessments are collected within 20 days before or on the day of study treatment administration. Summaries for age by group (< 65 and \geq 65), sex, ethnicity, and race will be provided. Baseline height, weight and employment status will also be summarized. CDI history will be summarized by total number of episodes experienced prior to treatment. Additionally, the following will be summarized for each episode of CDI: duration (days), treatment administered, hospitalization with duration (if applicable) and available *C. difficile* test results.

The following Baseline assessments will be provided in summary table and listings:

- Medical history

- CDI history
- Laboratory testing (hematology)
- Vital signs (systolic/diastolic blood pressure [mmHg], pulse rate [beats/min], respiration rate [breaths/min], temperature [°C])

6.4 Demographic and Other Baseline Characteristics

All Baseline summaries will include the SP, ITT, mITT, and PP populations. Descriptive statistics (number of subjects [N], mean, standard deviation [SD], median, interquartile range [IQR], minimum, and maximum for continuous variables and number of subjects [N] and the percentage for categorical variables) will be provided for all Baseline measures.

6.5 Prior and Concomitant Therapy

The World Health Organization (WHO) Drug Dictionary version 2017E B2 will be used to classify medications by preferred term and WHO Anatomical Therapeutic Chemical (ATC) at the highest level of ATC. Listings of all concomitant medications will be made by WHO ATC classification of ingredients and by preferred term. All listings of usage of medications will be based on the SP.

6.6 Safety Analysis

The SP will be used to summarize all adverse event data, unless otherwise specified. Safety data will be summarized for events after the first and second enemas, as well as combined. Events occurring after the first enema will be counted up to the date of retreatment, or study exit. Events on, or after, the date of a second enema will be assigned to the second period. The combined analysis will consider all events, after first enema through study exit, even if a subject receives a second enema.

6.6.1 *Analyses Supporting the Primary Safety Endpoint*

Assessment of the primary safety objective will include descriptive statistics and be performed on the SP. Additional sub-analyses of safety data may be performed on sub-populations.

6.6.2 *Other Safety Analyses*

6.6.2.1 *Adverse Events*

A summary of adverse events, TEAEs, non-serious TEAEs, and serious TEAEs will be summarized using counts of the number of events and frequencies (counts and percentages) of

the number of subjects. The incidence of each preferred term (PT) within the primary system organ class (SOC) as well as overall primary SOC incidence will be presented. Summaries may also be presented by PT, irrespective of SOC. A subject with multiple events coded to the same PT within a primary SOC will be counted only once for the PT within the primary SOC. Likewise, a subject with multiple events coded to the same SOC will be counted only once within the SOC.

An overall summary of AEs will present the incidence of (1) all TEAEs, (2) TEAEs related to IP, (3) TEAEs related to enema procedure, (4) TEAEs related to *C. difficile* disease, (5) TEAEs related to a preexisting condition, (6) serious TEAEs, (7) serious TEAEs related to IP, (8) serious TEAEs related to the enema procedure, (9) serious TEAEs related to *C. difficile* disease, (10) serious TEAEs related to a preexisting condition, and (11) TEAEs leading to death.

Frequency of occurrence and number and percent of subjects experiencing an event through 6 months follow-up will be presented for both the first and second enemas as follows:

- All TEAEs
- TEAEs by maximum severity
- TEAEs by relatedness to IP
- TEAEs by relatedness to *C. difficile* disease
- TEAEs by relatedness to enema procedure
- TEAEs by relatedness to preexisting condition
- TEAEs resulting in subject withdrawal
- TEAEs resulting in death
- Serious TEAEs
- Serious TEAEs by maximum severity
- Serious TEAEs by relatedness to IP
- Serious TEAEs by relatedness to *C. difficile* disease
- Serious TEAEs by relatedness to enema procedure
- Serious TEAEs by relatedness to preexisting condition
- Serious TEAEs resulting in subject withdrawal
- Serious TEAEs resulting in death

For the summary of AEs by maximum severity, if a subject has multiple events occurring in the same SOC or same PT, then the event with the highest severity will be counted. For AEs reported by causality, if a subject has multiple events occurring in the same SOC or same PT, the event with the highest association will be summarized.

A summary of TEAE and serious TEAE characteristics (severity, relatedness to IP, relatedness to *C. difficile* disease, relatedness to enema procedure, and relatedness to preexisting condition by outcome) will also be presented by first and second enema and overall.

Incidence of AEs and serious AEs will also be presented by onset interval separately for the first and second enemas (as applicable), as well as a combined presentation for the following intervals:

- Baseline (onset date prior to date of first enema)
- IP administration (onset date on the date of the first and second enema, as applicable)
- Intervals relative to the enema date (first and second enemas, as applicable):
 - 1-Week (day 8), 4-Weeks (day 29), 8-Weeks (day 57), 4 Months (Day 120), and 6 Months (Day 180).

For data presentation, SOC will be ordered alphabetically, with PT sorted by decreasing total frequency. No inferential statistics will be provided for the AE data.

Subject listings will be presented for all AEs including SAEs.

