5.3.4. Phase 3 Study Protocol 2017-01 Final Study Data

Study Design:

Study Protocol 2017-01 was a prospective, multi-center, double-blind, placebo-controlled Phase 3 study to evaluate the efficacy and safety of RBX2660 for the prevention of rCDI in 267 subjects randomized and treated in a 2:1 ratio to receive RBX2660 (Group B) or Placebo (Group A). The primary endpoint was the recurrence of CDI within 8 weeks of blinded treatment. The secondary endpoint was the loss of sustained clinical response through 6 months after blinded treatment. Safety endpoints included the number of AEs per subject, timing of attributable TEAEs, relatedness and severity of TEAEs.

Efficacy Results:

In total, 262 subjects had adjudicated outcomes for the primary endpoint in the mITT population. The primary statistical analysis used a Bayesian hierarchical model which formally incorporated data from a previous randomized Phase 2B study (Protocol 2014-01). RBX2660 demonstrated a 98.6% probability of superiority compared to Placebo in the prevention of CDI recurrence, with a success rate of 70.4% vs 58.1% through 8 weeks of blinded treatment. The posterior probability of superiority (0.986354) exceeded the threshold of 0.9750338 that controlled the Type I error rate at one-sided 0.025.

Sustained Clinical Response (Treatment Success at 8 weeks and no CDI recurrence for 6 months) was 90.6% (48/53) and 92.1% (116/126) in the Placebo and RBX2660 groups, respectively. Although there was no statistically significant difference between the two groups, the separation between RBX2660 and Placebo observed at 8 weeks was durable through 6 months.

Safety Results:

Of the 267 subjects in the safety population, 178 subjects (66.7%) reported a total of 708 TEAEs throughout the duration of the study; 478 TEAEs were reported by 154 (57.7%) subjects within 8-weeks of either treatment and 230 TEAEs were reported by 84 (31.5%) subjects more than 8-weeks after either treatment. More than a half (56.6%, 401/708) of TEAEs reported throughout the study occurred within 8-weeks of blinded treatment, which included solicited AEs collected during follow-up visits and telephone assessments and through Subject Diaries.

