6.6.2.5 Subject Diary including Solicited Adverse Events and Completion Compliance

All solicited adverse events recorded in the Subject Diary will be summarized utilizing frequencies (number of events), proportions (number of subjects with the event) and 95% CIs for categorical variables and using the descriptive statistics as listed in **Section 8.1** for continuous variables.

For each solicited event, severity scores will be summarized as both categorical and continuous values. For continuous summaries, severity scores will be identified as either pre-treatment or post-treatment (all diary entries captured after the first enema), and the average for each period will be calculated across individual subjects. Baseline for continuous summaries will be considered the average during the pre-treatment period. For categorical summaries, if a subject reports more than one severity score on the same date, the maximum severity will be used. Baseline for categorical summaries will be considered the last non-missing assessment prior to the enema.

For each categorical summary of event frequency, a two-sided 95% CI will be calculated using the normal approximation of the binomial.

The following summaries will be produced for the first enema:

- Frequency of severity scores on day of enema administration
- Frequency of severity scores on day 1 through 1-week post-treatment
- Frequency of maximum post-treatment severity score

Compliance in returning completed Subject Diaries will be calculated by dividing the number of diaries turned in, whether complete or not, by the number of diaries expected to be turned in. Furthermore, compliance will be summarized by calculating the proportion of subjects who turned in “complete” diaries, where complete is defined as answering all 14 daily questions (e.g.

11 solicited AE, Bristol Stool Type, New illnesses/injuries, New medications) for at least 80% of the expected number of diaries.

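### First-enema adverse event percentages keep retreated subjects in the denominator after they leave the period, so late first-enema incidence is understated

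*SAP*

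**What the plan says.** SAP 6.6 makes the Safety Population the default for adverse event data and sets up three analyses:

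- First enema: "Events occurring after the first enema will be counted up to the date of retreatment, or study exit".
- Second enema: "Events on, or after, the date of a second enema will be assigned to the second period".
- Combined: "The combined analysis will consider all events, after first enema through study exit, even if a subject receives a second enema".

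SAP 6.6.2.1 then says that "number and percent of subjects experiencing an event through 6 months follow-up will be presented for both the first and second enemas". It adds that "Incidence of AEs and serious AEs will also be presented by onset interval separately for the first and second enemas (as applicable", together with a combined presentation. Table 3 in SAP 5.2.1 sets the late onset intervals at days 58-121 and 122-180+. Major CDI complications (6.6.2.2) and new chronic conditions (6.6.2.4) are also summarised by enema.

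None of these sections gives a number at risk per period or interval, or a method that accounts for shortened follow-up. SAP 6.9 summarises the number of enemas and the time between them, but not time at risk. SAP 6.6.1 does not say which of the three analyses carries the primary endpoint. SAP 6.6.2.1 rules out inferential statistics for adverse events.

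Ascertainment differs between the periods. After the first enema there is a diary up to the 1-week visit, office visits at weeks 1 and 8, and calls at week 4 and months 4 and 6. After the second enema there are only calls, at weeks 1, 4 and 8 and month 6. The diary section (SAP 6.6.2.5) covers one enema: "The following summaries will be produced for the first enema".

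**The concern.** The numerator and denominator of the first-enema percentages cover different follow-up. A retreated subject can no longer contribute a first-enema event after retreatment, yet with the Safety Population as denominator still counts as a subject followed to 6 months without one. Retreatment is offered only to failures within 8 weeks, so the affected intervals are the late ones. That is where new chronic conditions and other delayed events would appear.

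The two enema periods will also be read against each other. The Protocol does this itself for study 2013-001 (section 5.3.1): it cites solicited events on Day 7 in 41.7% of subjects after two treatments against 51.5% after one. That study kept a diary after each treatment. This one keeps it only after the first, so the same reading here would partly reflect how events were collected.

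**Working it through.** The plan states no by-enema rate, so there is no planned figure to reproduce. The prior-study inputs in Protocol 5.3.4 check by division: 178/267 = 66.7% with any TEAE, 154/267 = 57.7% with one within 8 weeks, 84/267 = 31.5% with one later.

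**1. When retreated subjects leave.** Failure falls within 8 weeks (56 days) and retreatment within 21 days of failure determination: 56 + 21 = 77 days. Determination follows a visit and a central laboratory result (Protocol 10.13), so 77 is approximate and some lag can be added. Share of a 180-day follow-up lost per retreated subject: (180 - 77)/180 = 57.2%. With retreatment on day 28 (illustrative) it is (180 - 28)/180 = 84.4%.

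**2. How many are retreated (r = failure rate x uptake).**
- Failure: 1 - 0.789 = 21.1% (study 2015-01, Protocol 5.3.3) and 1 - 0.704 = 29.6% (study 2017-01, Protocol 5.3.4).
- Uptake: 15/16 = 93.75% (study 2013-001, Protocol 5.3.1).
- r = 0.211 x 0.9375 = 19.8% and 0.296 x 0.9375 = 27.8%, or about 148 and 208 of 750.
- Wider range: 0.296 x 0.50 = 14.8% (50% uptake is illustrative) and 0.50 x 0.9375 = 46.9% (the 16/32 first-treatment failure rate in 2013-001).

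**3. Follow-up lost, r x (180 - T)/180.** For retreatment on day T = 77: 11.3% at r = 19.8% and 15.9% at r = 27.8%. For T = 28: 16.7% and 23.4%.

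**4. Effect on the printed percentages.** The Protocol reports for 2017-01 that "230 TEAEs were reported by 84 (31.5%) subjects more than 8-weeks after either treatment". Suppose retreated subjects would have had the same risk and none of their later events counts for the first enema. The late percentage then prints as 31.5% x (1 - r). With a cut at week 8, the any-TEAE percentage prints as 66.7% - r x (66.7 - 57.7).

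| Retreated (r) | TEAE after week 8 (full: 31.5%) | Any TEAE (full: 66.7%) |
|---|---|---|
| 14.8% | 26.8% | 65.3% |
| 19.8% | 25.2% | 64.9% |
| 27.8% | 22.7% | 64.2% |
| 46.9% | 16.7% | 62.5% |

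The any-TEAE loss is thus 1.3 to 4.2 points; cuts before week 8 lose more. For late events the relative shortfall is at most r. It is about r in days 122-180+, where retreated subjects have no first-enema time. It is less in days 58-121, where they may contribute up to about 20 of the 64 days (58 to 77). Events confined to the first week are essentially all counted.

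**5. Second enema.** Follow-up runs a full 6 months, so truncation does not lower this rate. Late events from the first enema that start after retreatment push it up; telephone-only collection pushes it down by an amount the documents cannot size. The denominator is also unstated: with an assumed 50% event rate among 208 retreated subjects, 104/208 = 50% would print as 104/750 = 13.9% if the Safety Population were used.

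**6. Would a rate per person-month solve it?** Take r = 27.8%, T = 77 and 230/708 = 32.5% of events after week 8, spread evenly over days 57-181.
- Events lost: 0.278 x 0.325 x (181 - 77)/(181 - 57) = 7.6%.
- Person-time lost: 0.278 x (181 - 77)/181 = 16.0%.
- Rate ratio: (1 - 0.076)/(1 - 0.160) = 1.10.

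The person-time rate would be about 10% too high at identical risk, because events cluster early. In 2013-001, 66.5% of adverse events occurred by the 7-day visit.

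**The case against.** The tables are descriptive, no test between enemas is planned, and the combined analysis has no cut at retreatment. The primary endpoint can be read from that analysis. The onset-interval tables let a reader look at the early intervals, where little is lost. All of this stands, and it limits the point to late first-enema incidence. It does not cure the late intervals, where an uncorrected denominator does the most damage. SAP 7.1 bases categorical percentages on non-missing subjects, but does not say that a retreated subject counts as missing for later first-enema intervals.

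The inputs can also be challenged, and fairly. The 21.1% failure rate comes from a two-enema regimen. The 15/16 uptake comes from a 34-subject study with a ten-day retreatment window. The 2017-01 TEAE split pools RBX2660 and placebo and is timed from either treatment. The sizes are therefore illustrations; the mechanism does not depend on them.

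A reader might infer that both enema rates are understated. The documents do not support this for the second enema, as step 5 shows. A reader might also infer that solicited diary events are tabulated for both enemas side by side. They are not: the diary summaries are for the first enema only, and a diary entry becomes an adverse event only after assessment. Nor do the documents show that retreated subjects are the sickest group.

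**Conclusion.** The point holds for the first enema. Followed literally, SAP 6.6 and 6.6.2.1 understate first-enema incidence after week 8 by up to about the retreated share, 20-28% in relative terms under prior-study assumptions. That rests on retreated subjects having the same late risk as the others and on the Safety Population serving as the denominator. The any-TEAE bias is about 1-4 points with a week-8 cut over the wider range of r. First-week events and the combined analysis are essentially unaffected, so the documents do not support reading this as a threat to the primary endpoint, provided the combined analysis is named as its basis. The error in the second-enema rate has no determined direction. The first- and second-enema percentages are not like for like.

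**What to change.** 1. In the by-enema and onset-interval adverse event tables, and in the by-enema summaries of major CDI complications and new chronic conditions, use as denominator the subjects still in that enema period at the start of the interval, and print that number. For the second enema, use retreated subjects only.
2. For the first-enema 6-month figure, give a cumulative incidence censored at retreatment, or relabel it as running to retreatment or 6 months, whichever comes first. Retreated subjects are selected as failures, so a censored estimate should state that it assumes similar later risk.
3. State in SAP 6.6.1 that the combined analysis is the basis of the primary endpoint.
4. Footnote the by-enema tables: diary and office-visit ascertainment applies to the first enema only.
5. Do not rely on a constant person-month rate, for the reason shown in step 6.

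The cost is slightly more programming and longer tables. All dates needed are already collected. This is a cheap improvement.
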